2. Before participating in a study, you will be asked if you have any adhesive allergies and if you do, the reflective markers can be placed over tight-fitting clothing.
3. You may ask to remove the mouthpiece and nose clip, rest or stop at any time.
4. Significant efforts will be made to guard against the disclosure of confidential information. All data collected will be de-identified so that your identity is protected; however, the data collected poses no apparent risk to your privacy. We will implement a data and safety-monitoring plan to ensure your privacy. To de-identify your data, you will be given a unique code, and only the research team will have access to the key (linking the code to participant identifiers), which will be kept in a locked cabinet in a locked office. The key will be destroyed upon study completion.

E. Potential Scientific Problems:

Adjustments to PL, PAP, and CAL may not be significantly different from the standard prosthetic/bicycle configuration. In the unlikely event that we find the optimal configuration to be the same as the standard configuration, we will be more confident in the typical recommendations for bicycling and may not need to develop guidelines for optimizing efficiency and comfort. If we find this to be true, we will evaluate how robust this finding is across participants. Within our protocol, we will ask 15 patients with TTAs to complete a VAS and modified PEQ. We predict that use of different PLs, PAPs, and CALs will affect VAS and PEQ scores. We calculated a statistical power of >0.44 to detect a 10% difference in PEQ scores based on 15 participants and the largest standard deviations found in previous studies using the PEQ [23]. Therefore, we may not have adequate statistical power to detect a difference in comfort and fit.

F. Data Analysis Plan:

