We predict that different PLs, PAPs, and CALs will affect biomechanics, metabolic costs, and comfort/satisfaction. We calculated effect sizes [17] >0.86 , >0.995 , 0.97 , and >0.44 to detect 10% differences in efficiency (mechanical power/metabolic power), knee and hip joint range of motion, mechanical work output symmetry, and PEQ scores, respectively, based on 15 participants, a repeated measures design, $\alpha=0.05$, and standard deviations found in previous studies [11, 13, 18, 19]. Thus, we feel we have an adequate sample size to detect biomechanical and metabolic differences in our proposed studies, but may not have adequate power to detect differences in PEQ scores.

G. Summarize Knowledge to be Gained:

The proposed research is highly relevant to and will benefit Veterans with transtibial amputations (TTAs). The goal of our research is to challenge the state-of-the-science by developing evidence-based prosthetic and bicycle fit guidelines that optimize the biomechanics, metabolic costs, efficiency and comfort/satisfaction for Veterans with TTAs. Optimizing these parameters through changes in prosthetic and bicycle configurations (i.e. pylon length (PL), pedal attachment position (PAP) beneath the forefoot versus the pylon, and crank arm length (CAL)) will improve rehabilitation and benefit Veterans with TTAs by minimizing injury risk and pain/discomfort, and maximizing physical activity and function; thus facilitating their return to an active healthy lifestyle and/or active duty.

H. References:

1. Ziegler-Graham, K., et al., *Estimating the prevalence of limb loss in the United States: 2005 to 2050*. Arch Phys Med Rehabil, 2008. **89**(3): p. 422-9.
2. US Department of Veterans Affairs, *Fact Sheet. VA Achievements in Diabetes Care, February, 2006*, 2006, <http://www1.va.gov/opa/fact/diabtsfs.asp>.
3. Sambamoorthi, U., et al., *Initial nontraumatic lower-extremity amputations among veterans with diabetes*. Medical Care, 2006. **44**(8): p. 779-787.
4. Ziegler-Graham, K., et al., *Estimating the prevalence of limb loss in the United States: 2005 to 2050*. Archives of Physical Medicine and Rehabilitation, 2008. **89**(3): p. 422-429.
5. Fischer, H., *U.S. Military Casualty Statistics: Operation New Dawn, Operation Iraqi Freedom, and Operation Enduring Freedom*, 2010, <http://www.fas.org/sqp/crs/natsec/RS22452.pdf> Congressional Research Service.

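### Section IV.E would take a non-significant difference from the standard fit as support for that fit, for comfort as well as efficiency, with no margin or confidence-interval criterion for sameness

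*Combined protocol and SAP*

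**What the plan says.** Section IV.E opens with the possibility of a null result: "Adjustments to PL, PAP, and CAL may not be significantly different from the standard prosthetic/bicycle configuration". The next sentence restates this as sameness, "In the unlikely event that we find the optimal configuration to be the same as the standard configuration", and draws the consequence that "we will be more confident in the typical recommendations for bicycling and may not need to develop guidelines for optimizing efficiency and comfort". One safeguard follows: "If we find this to be true, we will evaluate how robust this finding is across participants". No metric or threshold is attached to it.

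The same paragraph then turns to comfort. It reports that "We calculated a statistical power of >0.44 to detect a 10% difference in PEQ scores based on 15 participants" and concludes: "Therefore, we may not have adequate statistical power to detect a difference in comfort and fit". Section IV.F (Data Analysis Plan) repeats the caveat, that the study "may not have adequate power to detect differences in PEQ scores", and gives the figures for the other outcomes: "We calculated effect sizes [17] >0.86 , >0.995 , 0.97 , and >0.44 to detect 10% differences in efficiency", knee and hip range of motion, work symmetry and PEQ, in that order.

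The analysis methods, at the end of section IV.A, are repeated measures ANOVA at the 0.05 level, with Bonferroni adjustment where needed, and linear mixed models for Aim 1. The ANOVA is also the stated means of finding the best combination of pylon length, pedal position and crank length. No equivalence margin, equivalence test or confidence-interval rule appears anywhere.

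**The concern.** The paragraph takes three steps: no significant difference, then sameness, then more confidence in the standard fit. The first step does not hold. Failing to reject can mean that there is no effect or that the estimate is too imprecise to show one, and the plan has no criterion to tell these apart. A consistency check across participants does not supply it, because it sets no limit on how large an undetected mean difference could be.

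The conclusion names efficiency and comfort, the two outcomes with the lowest stated power. For comfort the paragraph itself says that power may be inadequate, yet it does not carry that admission over to how a null comfort result should be read. At stake is an endorsement of the typical fit on comfort that the data could not support, and a possible reason to hold back the guidelines that are the product of Specific Aim 2.

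**Working it through.** **Inputs.** n = 15 and α = 0.05 (IV.F). Stated power for a 10% difference: PEQ >0.44 (IV.E and IV.F); efficiency >0.86, work symmetry 0.97, range of motion >0.995 (IV.F). IV.F calls these figures effect sizes, but IV.E calls the PEQ figure statistical power, and that reading is used here. Sidedness, SDs and within-subject correlation are not given, so the plan's powers cannot be reproduced forward. I assume a two-sided paired t test of one configuration against standard and work backwards.

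**Step 1: implied precision.** Find the standardised paired difference dz for which a noncentral t with 14 df and noncentrality dz × √15 gives the stated power. Then the SD of the paired difference is 10%/dz, and the 95% CI half-width is 2.145 × SD/√15.

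- PEQ: dz = 0.501, noncentrality 1.94, SD = 19.9%, half-width = 2.145 × 19.94/3.873 = 11.0%.
- Efficiency: dz = 0.845, noncentrality 3.27, SD = 11.8%, half-width = 2.145 × 11.84/3.873 = 6.6%.

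**Step 2: how often a real difference is non-significant.**

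| Outcome | Stated power, 10% | Missed at true 10% | Power at true 5% |
|---|---|---|---|
| PEQ | >0.44 | up to 1 − 0.44 = 56% | 0.15 |
| Efficiency | >0.86 | up to 1 − 0.86 = 14% | 0.33 |
| Work symmetry | 0.97 | 3% | 0.49 |
| Range of motion | >0.995 | under 0.5% | 0.62 |

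Where the plan gives a lower bound on power, the miss rate is an upper bound and the 5% figure is the value at that bound.

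**Step 3: effect of a Bonferroni adjustment.** The plan does not state the number of comparisons. For illustration, 3 comparisons lower power at a true 10% difference to about 0.70 (efficiency) and 0.26 (PEQ); 6 lower it to 0.59 and 0.18.

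**Step 4: what an interval criterion would deliver.** Call a configuration similar to standard if the 90% CI of the paired difference lies within ±M (two one-sided 5% tests). The 90% half-width is 1.761 × SD/√15, which is 9.1% for PEQ and 5.4% for efficiency. With M = 10%, a PEQ estimate with that half-width must lie within 10 − 9.1 = 0.9 percentage points of zero to qualify; an efficiency estimate must lie within 10 − 5.4 = 4.6. Allowing for sampling variation in the SD, the chance of meeting the criterion when the true difference is zero is:

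| Outcome | M = 10% | M = 5% |
|---|---|---|
| PEQ | 0.20 | 0.00 |
| Efficiency | 0.86 | 0.07 |
| Work symmetry | 0.98 | 0.28 |
| Range of motion | 0.997 | 0.51 |

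**The case against.** The strongest reply is that the condition is not non-significance at all. Specific Aim 1 and section IV.B describe the optimal pylon length as the most efficient one, so the optimum being the same as standard could mean that the standard fit gave the best observed efficiency. That would be a positive finding, and a much rarer error: by the normal approximation, a configuration truly 10% better would average worse than standard about 0.05% of the time for efficiency (noncentrality 3.27) and 2.6% for PEQ (1.94). This reading is possible. Against it, the preceding sentence is about significance, and section IV.A names ANOVA as the way to determine the optimum. Even if it is right, sameness still has no precision criterion, and an optimum chosen on efficiency would not support a conclusion about comfort.

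Several stronger inferences should be resisted:

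- **That the study is underpowered in general.** It is not, for 10% differences in symmetry or range of motion, and stated power for efficiency is >0.86. The weakness is chiefly comfort. The plan discloses it twice, and IV.E says the PEQ calculation used the largest SDs from previous studies.
- **That this is a binding rule under which Aim 2 will be dropped.** The text is a hedged contingency: the event is called unlikely, guidelines may not be needed, and a robustness check is promised.
- **That the miss rates are the chance of this contingency arising.** They apply to one contrast. Several configurations are compared with standard, and one missed contrast does not make standard the optimum.
- **That PEQ cannot show similarity at n = 15.** It could, about 20% of the time at ±10% if the true difference is zero. Unlikely is the right word.

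**Conclusion.** The point holds, and chiefly for comfort. Followed as written, section IV.E could turn a non-significant PEQ result into confidence in the typical fit, although a true 10% difference would be missed up to about 56% of the time and the 95% CI would extend about 11% either side of the estimate. For efficiency the risk is modest at 10% (missed up to about 14%) but real for smaller effects (power about 0.33 at a true 5%).

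These figures rest on a two-sided paired t test, on reading the stated values as power, and on taking power at its stated bound; actual precision could be better. If 0.44 were a paired effect size instead, PEQ power would be about 0.36, so the conclusion on comfort would not soften. The Bonferroni figures depend on assumed numbers of comparisons and are not needed for the conclusion.

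A reader might go further and infer that any null result from this study would be uninformative. The documents do not support that: at the stated powers, null results on symmetry and range of motion would usually exclude a 10% difference.

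**What to change.** Replace the contingency sentence in section IV.E so that non-significance is not read as support for the standard fit. Specifically:

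1. For each outcome, report the CI of each paired difference from standard.
2. Conclude that a configuration is similar to standard on an outcome only if the 90% CI lies within a margin fixed and justified in advance. The plan's 10% planning difference is one candidate, but it was chosen as a detectable difference and needs its own justification as a margin. The choice matters: for efficiency, moving from 10% to 5% lowers the chance of meeting the criterion from 0.86 to 0.07.
3. Otherwise report the result as inconclusive, with its CI.
4. Remove comfort from the stated conclusion unless the PEQ result meets the criterion, and say in advance that with 15 participants it is unlikely to (about 20% of the time at ±10% if the true difference is zero, at the stated power bound).
5. Give the robustness check a metric, or present it as descriptive.

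The cost is a few sentences and one interval per contrast, with no new data. The downside is that some null results, probably most of those on PEQ, must be reported as inconclusive.

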Prosthesis Evaluation Questionnaire (PEQ). We will use repeated measures analysis of variance (ANOVAs) (significance at $\alpha < 0.05$) with Bonferroni corrections as needed for multiple comparisons to compare data between groups and between legs and determine the optimal PL/PAP/CAL combination (JMPIN, SAS Institute, Cary, NC). We will analyze results from Specific Aim 1 using linear mixed models. We will use a multiple regression and/or principal component analysis to develop optimal prosthetic/bicycle fit guidelines for Veterans with TTAs in Specific Aim 2.

Description of Population to be Enrolled:

We will recruit 15 Veterans with unilateral TTAs who are at or above a K3 Medicare functional classification level (MFCL), and who are 18-55 years old from the VA Jewell Clinic, locally, and nationally. Subjects will give informed consent prior to participation. A K3 MFCL means that a person has the ability or potential for ambulation with variable cadence. A person at K3 MFCL is a typical community ambulator who has the ability to traverse most environmental barriers and may have vocational, therapeutic or exercise activity that demands prosthetic use beyond simple locomotion. Subjects will have no known neurological disease or disorder, and will have no musculoskeletal injuries beyond an amputation. These inclusion/exclusion criteria will minimize any potential confounding variables, thereby increasing the internal validity of the proposed studies. Any person matching the inclusion criteria of the study, regardless of race or gender, will be recruited to participate.

Women and/or minorities will be included in the proposed study. Anyone matching the inclusion criteria of the study, regardless of race, sex, or ethnicity will be recruited to participate.

B. Study Design and Research Methods

Before participants are enrolled in each study, we will complete a pre-screening form and each participant will be asked to give informed written consent. We will ensure that all participants understand the consent form and protocol prior to participation.

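### The Data Analysis Plan prints its power values as effect sizes, and gives no power for the Bonferroni-corrected comparisons or mixed models that will identify the optimal fit

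*Combined protocol and SAP*

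**What the plan says.** Section IV.F (Data Analysis Plan) gives the sample-size justification: "We calculated effect sizes [17] >0.86 , >0.995 , 0.97 , and >0.44 to detect 10% differences in efficiency", followed by knee and hip range of motion, mechanical work symmetry and PEQ scores. The stated basis is 15 participants, a repeated measures design, alpha 0.05 and "standard deviations found in previous studies [11, 13, 18, 19" (references 11, 13, 18 and 19). It concludes: "Thus, we feel we have an adequate sample size to detect biomechanical and metabolic differences in our proposed studies". The PEQ is then excepted, in a clause that shows which quantity the authors have in mind: "but may not have adequate power to detect differences in PEQ scores".

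Section IV.E (Potential Scientific Problems) reports the PEQ value differently: "We calculated a statistical power of >0.44 to detect a 10% difference in PEQ scores based on 15 participants", using "the largest standard deviations found in previous studies using the PEQ [23" (reference 23). The reference list ends at 19.

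Section IV.A (Outcome Measures) plans repeated measures ANOVAs at the 0.05 level "with Bonferroni corrections as needed for multiple comparisons to compare data between groups and between legs and determine the optimal PL/PAP/CAL combination". It then adds: "We will analyze results from Specific Aim 1 using linear mixed models". Specific Aim 1 and Section IV.B describe four pylon lengths, four crank arm lengths (counting the reference length) and two pedal attachment positions. The number of comparisons to be corrected is not stated.

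**The concern.** There are two separate faults and one ambiguity.

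**Label.** An effect size and a power are different quantities. As printed, the paragraph that justifies 15 participants cannot be checked or reused.

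**Scope of the adequacy claim.** The optimal configuration is to be chosen among several levels, by comparisons that may be tested below 0.05. The power statement stops at 0.05 and does not say whether it carries over to the mixed models. Efficiency matters most, because the plan equates the optimal pylon length with the most efficient one. If power for the deciding comparison is low, a real 10% difference could be missed.

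**Meaning of a null result.** Section IV.E opens with adjustments that may not differ significantly from standard. It then says the team would gain confidence in the usual recommendations if the optimal and standard configurations coincide. This can be read as letting non-significance count in favour of the standard fit, including for comfort, where low power is conceded.

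**Working it through.** **1. Which quantity is printed?** The PEQ value has the same size (>0.44), target (10%) and sample size (15) in both sections, and Section IV.E names it as power. For the other three values this is an inference. They share the sentence, the effect is already fixed at 10%, they are said to depend on n and alpha, the cited source is power software, and the conclusion speaks of adequate power. As a cross-check, a paired standardised difference of 0.44 with n = 15 (two-sided 0.05) gives power of about 0.36, which does not match Section IV.E.

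**2. Can the values be reproduced?** No. No SD, mean or within-subject correlation is given. I therefore solve backwards from the printed values, treating each as exact, although three are lower bounds. Assumptions of mine: the type of test, 3 comparisons (each level against the initial fit) or 6 (all pairs of four levels), and 0.80 as a benchmark.

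**3. Paired reading.** Power = P[F′(1, 14; λ) > F critical at alpha], with λ = 15·dz². Solve for dz at 0.05, then recompute at 0.05/3 = 0.0167 and 0.05/6 = 0.0083.

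| Outcome | Printed | dz | 3 comparisons | 6 comparisons |
|---|---|---|---|---|
| Efficiency | 0.86 | 0.845 | 0.705 | 0.590 |
| Work symmetry | 0.97 | 1.069 | 0.904 | 0.835 |
| Range of motion | 0.995 | 1.263 | 0.976 | 0.948 |

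For corrected power of 0.80, uncorrected power must be at least 0.919 (3) or 0.959 (6).

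**4. Four-level omnibus reading.** Noncentral F with 3 and 42 df, assuming sphericity. Power of 0.86 gives λ = 13.87. If the largest difference is d, then λ = 15·c·d²/σ², where c depends on the pattern of means. The contrast between the extreme levels has λ_c = 15·d²/(2σ²) = λ·0.5/c, on 1 and 42 df.

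| Pattern of means | c | λ_c | Efficiency, 3 / 6 | Omnibus power needed for corrected 0.80, 3 / 6 |
|---|---|---|---|---|
| Other levels midway | 1/2 | 13.87 | 0.885 / 0.824 | 0.771 / 0.841 |
| Evenly spaced | 5/9 | 12.48 | 0.845 / 0.773 | 0.818 / 0.880 |
| One level differs | 3/4 | 9.24 | 0.706 / 0.609 | 0.923 / 0.959 |
| Two equal pairs | 1 | 6.93 | 0.559 / 0.455 | 0.978 / 0.991 |

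On the same reading, symmetry runs from 0.980 / 0.962 (midway) to 0.773 / 0.684 (two pairs), and stays above 0.80 in the other three patterns. Range of motion is never below 0.897 / 0.839.

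**5. Slope reading.** If pylon or crank arm length enters a model as one linear term and the means are evenly spaced, the slope carries all of λ = 13.87 on 1 and 42 df. Power at 0.05 is about 0.95, with no pairwise correction.

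**6. What a null PEQ result could exclude.** On the paired reading, power of 0.44 gives dz = 0.501, so the SD of differences is 10%/0.501 = 19.94%. The 95% CI half-width is 2.145 × 19.94/√15 = 11.0%. It falls below 10% only if true power exceeds about 0.515.

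**The case against.** The label is largely editorial: Section IV.E has it right, and no design decision turns on the word. The citation slip is clerical. Both points stand as to weight, but both errors remain in print.

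A reader might infer that 0.05 is the wrong alpha. The documents do not support that. An omnibus repeated measures ANOVA at 0.05 is what Section IV.A plans, Bonferroni applies only as needed, and powering the omnibus test is common practice. No stated number is shown to be wrong.

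A reader might also infer that the trial is underpowered for efficiency. That is not supported either. The test, SDs and comparison count are unknown, 0.86 is a lower bound, and the illustrations fall on both sides of 0.80. A slope model would do well, and repeating the pylon lengths under both pedal positions could add precision that I have not counted. What remains is that the documents do not say which of these cases applies.

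Finally, a reader might infer that the team will accept the standard fit on the strength of non-significance. The text does not commit to this. Optimal pylon length is glossed as most efficient, which is a ranking; the null outcome is called unlikely; a robustness check across participants is promised; and low PEQ power is admitted. The wording is ambiguous, not a stated decision rule.

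**Conclusion.** The mislabel is established for PEQ and a strong inference for the other three values. It is also established that no power is given for the corrected comparisons or for the mixed models, so adequate sample size for efficiency is not demonstrated for the analysis that selects the configuration. Inadequacy is not demonstrated either. Treating 0.86 as exact, corrected power is 0.71 or 0.59 on the paired reading and about 0.46 to 0.89 on the omnibus reading, against about 0.95 for a slope. Range of motion looks safe under every reading tried, and symmetry under all but the two-equal-pairs pattern. All of this rests on my assumed tests and comparison counts. The weight is minor to moderate: a cheap correction to the sample-size justification, with no change to the design.

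**What to change.** **Section IV.F**
- Replace the effect-size label with power, once the team confirms this for all four values.
- Name the test and give the SDs used.
- State that the values hold at an uncorrected alpha of 0.05.
- Add power for the comparison or mixed-model term that will select the optimal configuration, at its corrected alpha and with the comparison count if Bonferroni is used.
- Limit the adequacy claim to the outcomes that keep it.

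**Section IV.E**
- Correct citation [23] and keep the robustness check.
- Add: *A non-significant difference will not by itself be taken as support for the standard configuration; estimated differences will be reported with confidence intervals at the same multiplicity level as the tests, and a non-significant result whose interval includes a 10% difference will be called inconclusive.* The 10% is the plan's own target. The rule is confined to non-significant results so that a significant gain of about 10% is not called inconclusive.

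**Cost.** Text edits and one re-run of the power calculation with SDs the team should already hold. The stated efficiency power may look less favourable. No extra participants are needed.
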